We will also collect de-identified routine data from participating facilities. These records reflect routine programmatic data collected by the Malawi Ministry of Health or Tingathe. Data will be abstracted retrospectively. These records will include a) facility-level HIV testing registers, b) contact registers and c) index registers. Data from these sources will be used to inform our assessment of service uptake outcomes.

Management

Paper-based records will be stored in locked filing cabinets in locked rooms. Electronic data will either be collected using an encrypted electronic device or entered into a password-protected database by a trained data entry clerk. Electronic data will be stored on secure, password-protected servers.

Analysis

For **Aim 1**, we will compare health worker fidelity to ACT counseling procedures between the enhanced and standard implementation arms. We have $>99\%$ power to detect a difference in fidelity outcomes between arms.

For **Aim 2**, we will compare HIV service uptake outcomes between the enhanced and standard implementation arms. Outcomes will include indexes who participate in ACT, contacts elicited, HIV self-test kits distributed, contacts tested, and contacts identified as HIV positive. We have $\geq 80-85\%$ power to detect a difference in each of the outcomes of interest between randomization arms.

For **Aim 3**, we will compare the cost-related outcomes between the enhanced and standard implementation arms through cost-effectiveness analyses.

Risks/benefits to subjects

Risks: Risks are minimal for health workers and patients. For individuals participating in this study, there is a potential risk of breach of confidentiality as well as a risk of discomfort related to participation. Breach of confidentiality may occur if unique identifiers in datasets are linked back to personal identifiers. This is highly unlikely and measures will be taken to ensure that this does not occur. There is also a risk of discomfort with participation, but this is expected to be rare and minor.

Benefits: Health workers may gain new knowledge and skills that make them better ACT providers or enhance their counseling skills. They may also enjoy the different study activities, such as discussing the ACT program in focus groups or interviews. Individual patients may enjoy exit interviews. This research is designed to create generalizable knowledge and enhance HIV programs in Malawi.

Costs/compensation

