Recruitment of patients (indexes and contacts) is expected to occur at each facility during the study period. The study team will be assigned to spend time at each facility and will approach potential indexes and contacts about participation in the study. Study team members will be trained in effective communication techniques and will engage the potential participants in brief conversations about the purpose, nature, and duration of the study. If interested, potential participants will be offered the opportunity to provide informed consent, and those who consent will be enrolled.

Procedures

	Pre	Q0	Q1	Q2	Q3	Q4	Q5	Q6	Q7	Q8
Facility survey (FS)		X								
SOC training	X									
Data harmonization		X								
Randomization		X								
Enhanced training Adoption/adherence (AD)		11 clusters					11 clusters	11 clusters		
SOC implementation			X	X	X	X	X	X	X	X
Enhanced implementation			11 Clusters	11 clusters	11 clusters	11 clusters	22 clusters	33 clusters	33 clusters	33 clusters
Service uptake			X	X	X	X	X	X	X	X
HCW consent	X									
HCW surveys	X		X			X				
Simulated fidelity		X	X							
Authentic fidelity			X	X	X	X				
Exit interviews			X	X	X	X				
Time and motion			X	X	X	X				
Focus groups/in-depth interviews	~8 clusters		~8 clusters				~8 clusters			

Facilities will participate in the following procedures:

Pre-trial

- All sites will have standard of care training

Quarter 0

- A facility survey will be conducted
- Data harmonization will occur to ensure all facilities are collecting the same data in the same way.
- All facilities will be randomized to one of the two study arms
- 11 sites randomized to the enhanced arm will receive enhanced blended learning training package

Quarters 1-4

- All ACT procedures will be conducted and service uptake data will be collected
- All clusters will receive standard of care implementation
- 11 clusters will receive enhanced implementation

Quarters 5-8

- All ACT procedures will be conducted and service uptake data will be collected
- 11 clusters randomized to the standard arm will receive enhanced package (Q5)
- 11 clusters randomized to the standard arm will receive enhanced package (Q6)

Health care workers (e.g. HDAs, CHWs, etc.) will participate in the following procedures:

Pre-trial

- At the time of recruitment, health workers will be offered the opportunity to provide informed consent. Those who provide informed consent will complete the remaining study procedures.

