Health care worker (provider) survey	-Demographics, cadre, technology literacy, knowledge, attitudes, practices, aptitudes, past training, time spent on ACT activities	All enrolled health care workers (N=33 clusters x ~2+ HCWs/cluster=66+)	PRE Q.1 Q.4	Provider survey (SurveyCTO)
Focus group discussions (FGDs)/In depth interviews (IDIs)	-Learn about HCW feasibility and acceptability Compare SOC to ENH and PRE/Q1/Q4	Health care workers (N=8 groups x 3 times~=24 FGDs) (N=3 IDIs x 8 facilities x 3 times~=72 IDIs)	PRE Q.1 Q.4	Semi-structured guides (audio recording) (Survey CTO to document participants and timing)
Fidelity Assessments (FA)	-Observe HCW conducting true index and/or contact encounters	Health care workers, indexes, contacts ((N= 33 cluster x minimum of 2 indexes/cluster=66-600) (N= 33 cluster x minimum of 2 contacts/cluster=66-200)	Q.1-4	Fidelity assessment tool (audio recording to paper to SurveyCTO)
Index exit interviews Contact exit interviews (Xls)	-Examine index acceptability -Examine contact acceptability	Indexes and contacts: (N= 33 cluster x minimum of 2 indexes/cluster=66-600) (N= 33 cluster x minimum of 2 contacts/cluster=66-200)	Q.1-4	Index exit interview (SurveyCTO)
Time and motion assessment (TM)	-Assess the effort to which HCWs work on each activity	Health care workers N=(~2-3/cluster x 33 facilities=66-100 days of observation)	Q.1-4	Time and motion survey (paper to SurveyCTO)
Effectiveness outcomes (EF)				
Total potential indexes	#ART patients who were supposed to be assessed per quarter plus the #new HIV+ patients per quarter	N=33 clusters x 8 quarters=264	Q.1-8	ART and HTS registers HTS registers (register to SurveyCTO)
# indexes, #contacts elicited, # STKs distributed	Number of indexes captured, contacts elicited and STKs distributed	N=33 clusters x 8 quarters=264	Q.1-8	Index and contact registers
# contacts tested # HIV+ contacts	Number of contacts returned and the proportion HIV+	N=33 clusters x 8 quarters=264	Q.1-8	Index and contact registers

Evaluation framework

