Outcomes of interest: Five ACT service uptake outcomes will be measured from index and contact registers on a quarterly basis. Each of these outcomes will be measured as a count per cluster per calendar quarter (three-month period). We will use facility-level data because the facility (i.e. cluster) is the primary unit of randomization. With 33 clusters under observation for four quarters, the facility-level dataset for the primary analyses will contain 132 observations (33 clusters * 4 quarters), 44 observations in the enhanced arm and 88 observations in the standard arm. The full two-year analyses will contain 264 observations (33 clusters * 8 quarters). The following measures will be calculated on a quarterly basis:

- **Total potential indexes:** This is the total number of ART and HTS patients that should be screened for and potentially offered ACT.
- **1: Indexes who participate in ACT:** The number of indexes in the index register.
- **2: Number of contacts elicited:** The number of contacts listed by the participating indexes. Are they put into the index register here?
- **3a: Number of self-test kits distributed:** The number of HIV self-test kits given to indexes for secondary distribution. Often, this is used as a method for testing contacts, rather than presenting to the clinic.
- **3b: Number of contacts tested:** The number of contacts with a recorded HIV test result. These tests are typically performed by a health care worker.
- **4: Number of contacts diagnosed HIV-positive:** The number of contacts in the contact register with an HIV-positive test result.

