Standard power formulas were not equipped for this cluster RCT design due to contingencies in the count outcomes with differing cluster sizes, repeated measures and within-facility correlated data. Thus, for power calculations in Aim 2, we applied these parameters to a simulation study of these facilities in SAS v9.4.^{87, 88} The number of total potential indexes per facility per quarter was accounted for as a statistical offset term.⁸⁹ The number of total potential

indexes per facility per quarter was generated from a Poisson distribution with a cluster-specific mean. Count values per cluster per quarter for each of 5 outcomes were generated from a negative binomial distribution with the random intercept variance, over-dispersion parameter, and arm-specific rates specified using a generalized linear mixed effects model with a log link. The Poisson facility-specific means, random intercept variances negative binomial over-dispersion parameters, and mean values for the standard arm were estimated from background data. To compute power, the simulated study data were analyzed using a negative binomial mixed-effects model accounting for repeated measures within a cluster. Statistical power was computed using simulation studies of 10,000 cluster RCT datasets. Based on these assumptions, and a significance level $\alpha=0.05$, we have **80-85% statistical power to detect a difference between the arms for each of the outcomes of interest**.

		Assumed values for empirical power calculations:							Statistical Power	
TPI denominators		Endpoint Rates		Effect size	Expected counts		Nuisance parameters			
Key measures:		Enhanced	Standard	RR	Enhanced	Standard	RIV	Scale		
0. Total potential indexes		n/a	n/a	1	407	407			n/a	
1. Total indexes		0.3100	0.2113	1.47	126	86	0.0981	0.0854	85%	
2. Contacts Elicited		0.3700	0.2383	1.55	151	97	0.1268	0.1880	81%	
3a. Self-test kits distributed		0.0650	0.0295	2.20	26	12	0.0001	1.9077	82%	
3b. Contacts Tested		0.1247	0.0614	2.03	51	25	0.3340	0.2847	85%	
4. HIV+ Contacts Diagnosed		0.0155	0.0074	2.10	6	3	0.3334	0.3039	82%	

RR=rate ratio
RIV = random intercept variance; estimated variance of the random intercept for cluster j
Scale parameter for the negative binomial mixed-effects model summarizes over-dispersion
Standard arm counts calculated by averaging background data from Oct 2019-April 2020 and Sep–Nov 2020
Nominal type I error rate of $\alpha=0.05$ is used throughout, with no adjustment for multiple endpoints

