Additional service uptake analyses from the trial (tertiary outcomes)

In addition to the primary analyses described above, rather than using total potential indexes as the statistical offset value, an indicator from the previous step of the cascade will be used. Power calculations were conducted for these secondary endpoints as well. The empirical power approach for rate ratios was described for the primary analysis. For proportion endpoints, a logistic mixed-effects model was used to simulate proportion values between [0, 1], and empirical power to detect a given risk ratio was calculated from a log-binomial mixed-effects model analysis.

		Assumed values for empirical power calculations:							Statistical Power	
Cascade Denominators		Type	Endpoint Rates		Effect size	Expected counts		Nuisance parameters		
Key measures:			Enhanced	Standard	RR	Enhanced	Standard	RIV	Scale	
0. Total potential indexes (TPI)			n/a	n/a	1	407	407			n/a
1. Total indexes (TI)	R	0.3100 per TPI	0.2113 per TPI	1.47	126	86	0.0981	0.0854	85%	
2. Contacts Elicited (CE)	R	1.4200 per TI	1.1279 per TI	1.26	179	97	0.0274	0.0658	83%	
3a. Self-test kits distributed	P	0.2250 per CE	0.1237 per CE	1.82	40	12	0.4260	n/a	83%	
3b. Contacts Tested	P	0.4400 per CE	0.2577 per CE	1.71	79	25	0.5770	n/a	82%	
4. HIV+ Contacts Diagnosed	P	0.0770 per TI	0.0349 per TI	2.21	14	3	0.5681	n/a	81%	

R = Rate; P = Proportion; RR = rate ratio for rates or risk ratio for proportions;
RIV = random intercept variance (i.e., estimated variance of the random intercept for each cluster)
Scale nuisance parameter for the negative binomial mixed-effects model summarizes over-dispersion for rate endpoints
Standard arm counts are per cluster per quarter and calculated by averaging background data from Oct 2019-April 2020 and Sep–Nov 2020
Nominal type I error rate of $\alpha=0.05$ is used throughout, with no adjustment for multiple endpoints

Temporal trend analyses

In addition to analyzing the primary cluster RCT data described above, we will explore temporal trends. Based on Figure 2, we will examine all of the indicators described above, comparing the periods preceding enhanced implementation (B+D) to the periods following enhanced implementation (A+C+E). Period A will also be compared to period C. In these analyses, the analytic procedures described for the primary and secondary analyses will be followed. These models will have terms for the primary exposure of interest and time.

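### No pre-randomization uptake quarter is scheduled and no endpoint's own baseline rate is named in the Aim 2 model, so available precision is given up, although baseline data exist

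*Combined protocol and SAP*

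**What the plan says.** - **Schedule.** In the data elements table (Effectiveness outcomes), total potential indexes and all five uptake counts are timed Q1-8: "N=33 clusters x 8 quarters=264". The Procedures section lists uptake collection only under Quarters 1-4 and 5-8: "All ACT procedures will be conducted and service uptake data will be collected".
- **Primary dataset.** Aim 2, Outcomes of interest: "132 observations (33 clusters * 4 quarters), 44 observations in the enhanced arm and 88 observations in the standard arm".
- **Enhanced-arm timing.** Under Quarter 0: "11 sites randomized to the enhanced arm will receive enhanced blended learning training package". Every scheduled uptake quarter in those clusters therefore follows training.
- **Model.** Aim 2, Analyses: a negative binomial mixed-effects model for Q1-4 with arm, an offset for log potential indexes, and key baseline variables. District is given as an example; no baseline outcome rate is named.
- **Stratification.** The Randomization section forms strata from district, facility type and baseline number of indexes identified.
- **Existing data.** The Protocol Summary says of the routine registers: "Data will be abstracted retrospectively". The primary power table notes: "Standard arm counts calculated by averaging background data from Oct 2019-April 2020" and September to November 2020. The text above that table says the facility-specific means, random intercept variances and over-dispersion parameters came from the same background data.

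**The concern.** Four of the five endpoints have large, persistent differences between facilities under the plan's own parameters. With 11 clusters against 22, chance can place better-performing facilities in one arm. Stratifying on the number of indexes does not guarantee balance on contacts tested or on HIV-positive contacts found. A cluster's own earlier rate is usually the strongest available predictor of its later rate, and here it can be had from registers or from data already held. If it is not planned for, the intervals are wider than they need be. A chance imbalance in an endpoint's own baseline is then not planned to be shown or adjusted for. If it is left under an open list of baseline variables, the choice may be made after the data are seen.

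**Working it through.** **1. Counts.** 33 × 8 = 264 and 33 × 4 = 132 (11 × 4 = 44 and 22 × 4 = 88). Both totals are used up by Q1-8 and Q1-4, leaving no room for an earlier quarter. From the Procedures table, pre-enhanced cluster-quarters are 22 × 4 + 11 (Q5) = 99, and enhanced ones are 11 × 4 + 22 + 33 × 3 = 165. All 99 come from standard-arm clusters. Figure 2 is not shown, so this count rests on the table.

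**2. Reproducing the stated power.** The inputs are the rates, random intercept variance (RIV) and scale in the primary power table, 407 potential indexes per cluster-quarter, and 11 versus 22 clusters. A two-sided 0.05 test is assumed, since sidedness is not stated. The variance of a cluster's mean log rate over four quarters is

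V = RIV + (scale + 1/μ)/4, with μ = 407 × rate.

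For contacts tested:
- Enhanced: μ = 407 × 0.1247 = 50.75; V = 0.3340 + (0.2847 + 0.0197)/4 = 0.4101.
- Standard: μ = 407 × 0.0614 = 24.99; V = 0.3340 + (0.2847 + 0.0400)/4 = 0.4152.
- SE(log RR) = √(0.4101/11 + 0.4152/22) = 0.2370.
- log RR = ln(0.1247/0.0614) = 0.7085; power = Φ(0.7085/0.2370 − 1.96) = 84.8%.

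| Endpoint | Stated | Formula | Simulation (300 trials) |
|---|---|---|---|
| Indexes | 85% | 84.5% | 87% |
| Contacts elicited | 81% | 81.1% | 79% |
| Self-test kits | 82% | 86.3% | 86% |
| Contacts tested | 85% | 84.8% | 86% |
| HIV-positive contacts | 82% | 83.7% | 83% |

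By the formula, four endpoints agree within 2 points. Self-test kits come out about 4 points higher here, probably because the cluster-specific means of potential indexes are not published and 407 was used throughout. The stated power is thus reproduced with no baseline term.

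**3. Share of noise that persists.** For contacts tested, RIV/V = 0.334/0.4152 = 0.80 in the standard arm. Before any benefit from stratification, the standard deviation of chance imbalance in the cluster effect is √(0.334 × (1/11 + 1/22)) = 0.213 on the log scale. A one-SD imbalance moves the rate ratio by a factor of e^0.213 = 1.24. HIV-positive contacts (RIV 0.3334) behave alike.

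**4. Gain from the endpoint's own baseline.** Assume four baseline quarters at the standard-arm rate, and let ρ be the correlation between a cluster's baseline and trial-period random effects. The documents give no ρ. Adjustment removes (ρ × RIV)²/V_b from each cluster's variance, with V_b equal to the standard-arm V. Estimating one slope multiplies the variance by about 1 + 1/30.

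Contacts tested, ρ = 0.5: (0.5 × 0.334)²/0.4152 = 0.0672. SE = √{[(0.4101 − 0.0672)/11 + (0.4152 − 0.0672)/22] × 31/30} = 0.2204, and 0.2204/0.2370 = 0.930.

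| ρ | Contacts tested: SE reduction (power) | HIV-positive contacts: SE reduction (power) |
|---|---|---|
| 0.3 | 1% (85.8%) | 1% (84.1%) |
| 0.5 | 7% (89.5%) | 5% (87.0%) |
| 0.7 | 16% (94.6%) | 11% (91.2%) |
| 0.9 | 30% (99.0%) | 21% (96.1%) |

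Break-even is at ρ of about 0.22 for contacts tested and 0.26 for HIV-positive contacts. For self-test kits the RIV is 0.0001, so nothing is removed and the SE rises by √(31/30) = 1.016, about 2%.

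**5. Fewer baseline quarters.** The background windows cover 7 + 3 = 10 months, a little over three quarters. Before the one-slope penalty, at ρ = 0.5, the SE ratio for contacts tested is 0.920 with three quarters, 0.915 with four and 0.947 with one.

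**The case against.** The best defence has four parts.

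- **The primary analysis needs no baseline.** Randomization makes the Q1-4 comparison valid, and the power was computed without one. This stands: a reader might infer bias or a power shortfall, and the documents support neither.
- **A baseline is used.** A reader might infer that no Aim 2 endpoint has one. That is wrong: baseline indexes identified is endpoint 1 and helps define the strata. The wording on baseline variables is also open-ended, so own-endpoint rates are unnamed, not excluded. What remains is that four endpoints have no planned baseline use and no model names one.
- **The gain may be small.** The background data have a gap from May to August 2020, and Q0 harmonization lies between them and the trial. A low correlation is plausible, and at 0.3 the gain is about 1%. District and the strata may already explain part of the variance, so the figures above are upper limits. This stands and is why a range is given.
- **The temporal analysis.** The enhanced clusters supply none of the B+D quarters, so one might add their earlier quarters to that set. The documents do not support this. All those quarters would predate harmonization and all the enhanced clusters' later ones would follow it, so a recording change could pass for an intervention effect. Nor does the plan promise before-and-after data in every cluster: this analysis is described as exploring trends, and the main control for the enhanced clusters is the concurrent randomized arm.

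**Conclusion.** The point holds as a matter of efficiency and prespecification. No pre-randomization uptake quarter is scheduled, no own-endpoint baseline rate is named in the Q1-4 model, and the means to supply one exist. Validity and the stated power are not in question. The cost of leaving the plan as it is runs from nothing (ρ near 0.2, or self-test kits) to an SE for contacts tested that could have been 16% smaller at ρ = 0.7 or 30% smaller at ρ = 0.9. For HIV-positive contacts the corresponding figures are 11% and 21%. These sizes rest on the plan's variance parameters, 407 potential indexes in every cluster-quarter, four comparable baseline quarters, an assumed ρ, and no prior gain from district or strata.

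**What to change.** - For all 33 clusters, abstract pre-randomization register counts and total potential indexes (four quarters where possible), or reuse the background counts already held. Use one source for every cluster, so that definitions are not mixed.
- Prespecify the log of each endpoint's own baseline rate as a cluster-level covariate in its Q1-4 negative binomial model for indexes, contacts elicited, contacts tested and HIV-positive contacts. Omit it for self-test kits.
- Replace the open list of baseline variables with a closed one, and report baseline rates by arm.
- Leave B+D as defined. At most, use baseline quarters from all 33 clusters in a sensitivity analysis, after checking comparability before and after the Q0 harmonization.

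The cost is one modest register pull, or none if held data are reused, and one degree of freedom per model. If pre-harmonization records are noisy, the covariate gains little. No participant contact is needed, and pre-randomization counts cannot be affected by arm.

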At each of the 33 clusters, at least 2 ACT encounters between health workers and indexes at least 2 ACT encounters between health workers and contacts will be audio-recorded. A minimum of 132 observations total are needed for both indexes and contacts (4/per cluster), but up to 200 contact encounters and 600 index encounters may be conducted. For indexes, attempts will be made to achieve balance between recruitment from the ART and HTS settings. For contacts, attempts will be made to achieve balance between the clinic and community settings.

Each audio-recording will be scored by two research officers blinded to the study arm and the two scores will be averaged. This tool has been field-tested.

Analyses: Generalized estimating equations (GEE) to account for potential correlation at the cluster level will be implemented to compare health worker fidelity scores between the enhanced and standard arms. Models with identity links and normal distributions will be used to compare means between the two arms. A working correlation structure will account for the correlated nature of observations from the same cluster. Models will contain a term for randomization arm. To assess fidelity maintenance over time, we will implement models with an interaction

term between time and randomization arm. To assess differences by setting (indexes: ART vs. HTS; contacts: clinic vs. community), we will implement an interaction term between randomization arm and setting. Indexes and contacts will be analyzed separately. Data from the authentic and simulated fidelity assessments (below) may be combined.

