Analyses: Data from quarters 1 through 4 (the cluster RCT design) will be analyzed using a negative binomial mixed-effects model accounting for quarterly repeated measures within each cluster. Models will use a log link, contain terms for randomization arm, and the natural-log transformed number of potential indexes will be incorporated as an offset term. Key baseline variables of interest, such as district, will be adjusted for. Rate ratios and 95% confidence intervals will be used to estimate the effect sizes and quantify the precision of effect estimates for the main analyses which will compare the enhanced versus standard arms for rates of each service uptake outcome per the total number of potential indexes (5 main endpoints denoted above). Secondary endpoints will take the same approach and use a negative binomial mixed effects model as well. Several secondary endpoints are proportion measures; for those endpoints effect size will be measured using a risk ratio and corresponding 95% confidence interval comparing the enhanced versus standard arms. To assess maintenance, interaction terms between quarters and randomization arm will be included to assess whether effects remain constant, intensify, or diminish over time during quarters 1 through 6.

Statistical power assumption, models, and estimates: Sample size calculations were guided by data from the 33 proposed clusters in the two districts from 2019-2020. In these two districts (Machinga and Balaka), Tingatthe supports 34 MOH facilities with implementation of the national HIV program and supervises approximately 150 community health workers and 100 HIV diagnostic assistants. Two nearby facilities in Balaka will be combined for analysis such that the 34 facilities are handled as 33 clusters.

Across these 33 clusters, 4600 persons are diagnosed with HIV each year and another 49,000 are already taking ART. From this, we estimated 35 new HIV-positive diagnoses per cluster per quarter and 372 ART patients per cluster per quarter or approximately 407 total potential indexes per facility per quarter. On average, of these 407 total potential indexes, there were approximately 86 indexes identified (0.21), 97 contacts elicited (0.24), 12 self-test kits distributed (0.03), 25 contacts tested (0.06), and 3 contacts diagnosed as HIV-positive (0.007). These values informed our assumptions for the standard arm.

Power for primary analyses:

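### The overall Aim 1 fidelity model names no setting term, although recordings are sampled by setting and balance is only attempted

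*Combined protocol and SAP*

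**What the plan says.** Under Aim 1, Primary outcome of interest (fidelity), at least two index and two contact encounters per cluster are to be recorded. The plan adds: "For indexes, attempts will be made to achieve balance between recruitment from the ART and HTS settings". A parallel aim covers clinic and community encounters for contacts. No target proportion is given, and balance is an aim rather than a quota.

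The Analyses paragraph compares mean fidelity by GEE with an identity link, separately for indexes and contacts. The only covariate it names for the overall comparison is arm: "Models will contain a term for randomization arm". Setting appears in one further place, a model with an arm-by-setting interaction meant to show differences by setting. No sampling weight is stated.

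The two sources of indexes can be read from the Data elements table, which defines total potential indexes as "ART patients who were supposed to be assessed per quarter plus the #new HIV+ patients per quarter". The Aim 2 power section gives the volumes: "we estimated 35 new HIV-positive diagnoses per cluster per quarter and 372 ART patients per cluster per quarter". The Randomization section says that facilities and staff know their arm, while coders of the recordings do not.

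**The concern.** A sample stratified by setting is compared between arms without setting in the model. Randomization does not protect the mix of recorded sessions, because sessions are chosen afterwards, during quarters 1 to 4. With a minimum of two index recordings per cluster, the achieved mix can easily miss its target. If it misses differently in the two arms, and ART and HTS sessions score differently, part of the setting gap is reported as an effect of the training.

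The plan's volumes give a reason to take this seriously. The enhanced package is expected to raise the number of indexes, while the power table holds potential indexes at the same number in both arms. The share of indexes who are newly diagnosed could therefore fall in the enhanced arm as a result of the intervention. What is at stake is a small, avoidable distortion of the primary Aim 1 estimate.

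**Working it through.** **1. Reproducing the plan's figures.**
- Volumes: "Across these 33 clusters, 4600 persons are diagnosed with HIV each year and another 49,000 are already taking ART". Per cluster per quarter, 4600/(33 × 4) = 34.8 (stated 35) and 49,000/(33 × 4) = 371.2 (stated 372).
- Indexes, from the primary Aim 2 power table ("0.3100 0.2113 1.47 126 86"): 407 × 0.3100 = 126 in the enhanced arm and 407 × 0.2113 = 86 in the standard arm.
- Aim 1 power: 132 recordings, 44 enhanced and 88 standard, SD 20.5, correlation 0.3, 4 per cluster. The design effect is 1 + 3 × 0.3 = 1.9. SE = 20.5 × √(1.9 × (1/44 + 1/88)) = 5.22. With two-sided α = 0.05 (assumed; not stated for Aim 1), power for 15 points is 82.0%, against a stated figure above 81%.

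**2. Can the natural mix differ by arm?** Take HTS indexes to be the new diagnoses, and suppose that every one becomes an index in the same quarter. This gives ceilings:
- Standard: 35/86 = 40.7%.
- Enhanced: 35/126 = 27.8%.
- Enhanced, adding the 3 extra positive contacts in the primary table ("0.0155 0.0074 2.10 6 3"): 38/126 = 30.2%.
- Enhanced, adding the 11 extra in the tertiary cascade table (14 against 3): 46/126 = 36.5%.

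All four are below 50%, and the enhanced ceilings lie below the standard one. These are arm averages and upper bounds, not expected shares. The documents give no comparable counts for clinic and community contacts.

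**3. Size of the shift.** Shift in the unadjusted arm difference = (HTS minus ART fidelity) × (HTS share enhanced minus HTS share standard). The documents give no fidelity by setting, so the gaps are assumed. The table shows absolute values in points.

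| HTS share, enhanced vs standard | Gap 5 | Gap 10 | Gap 20 |
|---|---|---|---|
| 50% vs 50% | 0 | 0 | 0 |
| 28% vs 41% (the ceilings) | 0.65 | 1.3 | 2.6 |
| 60% vs 40% | 1 | 2 | 4 |

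**4. Effect on type I error.** SE = 20.5 × √((1 + (m − 1) × 0.3)(1/n₁ + 1/n₂)).
- 66 index recordings (22 and 44, m = 2): SE = 6.10.
- 600 index recordings (200 and 400, m = 18.2): SE = 4.41.

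Type I error = P(|Z + shift/SE| > 1.96).
- Shift 1.3 points: 5.5% with 66 recordings, 6.0% with 600.
- Shift 2 points: 6.2% and 7.4%.
- Shift 4.5 points (a 30-percentage-point imbalance and a 15-point gap): 11.4% and 17.5%.

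The error grows with the number of recordings because the shift stays while the standard error falls.

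**The case against.** The strongest reply is that the plan already handles setting. It aims for balance, and if both arms reach the same mix the shift is exactly zero. It prespecifies an interaction model that yields arm differences within each setting. It says that models will contain an arm term, not that they will contain nothing else. The study team, not facility staff, approaches patients for recording, and the coders are blinded. Any shift also needs two conditions together, a setting gap and an unequal mix, and the likely values are small against planned differences of 15 to 30 points.

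Most of this stands and sets the severity. What it does not supply is a stated rule for the overall estimate when balance is missed. The interaction model is described as a way to assess differences by setting, not as the source of the primary result. Blinded scoring does not govern which sessions are recorded.

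A reader might go further and infer that a 50:50 sample is itself a fault, since it over-represents HTS sessions, and that results should be weighted by patient volume. The documents do not support that:
- The outcome is defined as health worker performance, not as the average experience of indexes. A common mix in both arms is a legitimate standard.
- The 50:50 result departs from one at the natural mix only if the training effect itself differs by setting. For an assumed 10-point difference in effect, the departure is 10 × (0.50 − 0.407) = 0.9 to 10 × (0.50 − 0.278) = 2.2 points.
- The protocol does not show that the index register holds ART or HTS origin. The available split, 35/407 = 9%, describes potential indexes, of whom about 21% become indexes.
- A 9% weight costs precision. With one recording per setting per cluster and correlation 0.3, the variance factor rises from 0.65 to 0.09² + 0.91² + 2 × 0.09 × 0.91 × 0.3 = 0.885. The interval widens by √(0.885/0.65) − 1 = 17%.

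**Conclusion.** The point holds as a minor one. The plan samples on setting, only attempts balance, and names no setting term in the overall Aim 1 model, so an unequal achieved mix would pass into the primary arm difference. In a moderate scenario (20-percentage-point imbalance, 10-point gap) the shift is 2 points and type I error is about 6% to 7%. With equal mixes there is no effect. The 17.5% figure needs a large imbalance, a large gap and all 600 recordings together, so it is not a likely result.

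The size rests wholly on assumed setting gaps and imbalances. The ceilings rest on reading HTS indexes as new diagnoses, which the definition of potential indexes supports. The documents do not show that the Aim 1 result will be biased, nor that balanced sampling is wrong. Because the natural mix may differ by arm, balancing protects the comparison.

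**What to change.** In the Aim 1 Analyses paragraph, state that the primary GEE contains arm and setting as main effects: ART/HTS in the index model and clinic/community in the contact model. Arms are then compared within setting. If the training effect differs by setting, the arm coefficient is an average of the within-setting differences. Keep the arm-by-setting interaction as the secondary model and keep the balanced sampling. Do not add volume weights. Reporting the achieved mix by arm would let readers see how much the adjustment mattered.

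The cost is one model term per analysis. Setting has to be recorded for the planned interaction in any case, so no new data are needed. The term may also gain some precision if scores differ by setting. It does not correct for differences between arms, within a setting, in which patients agree to be recorded.
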